#### 12. The research involves the following procedures conducted by and for what purpose:

	PERFORM	MED BY:	PROCEDURE IS:		
PROCEDURE	Research Staff	LSCDVAMC Clinical or Support Staff	Standard of Care*	For Research Purposes Only**	
Audiotaping / Videotaping	$\boxtimes$				
Attach VA Form 10-3203 REQUIRED ONLY FOR IN-PATIENT AND OUT-					

	PERFORM	MED BY:	PROCEDURE IS:			
PROCEDURE	Research Staff	LSCDVAMC Clinical or Support Staff	Standard of Care*	For Research Purposes Only**		
PATIENT SUBJECTS						
Biopsy						
Blood collection						
Chart review – prospective						
Chart review – retrospective						
Review of existing data (ex: registry, Database, etc.)						
X-ray or Ionizing radiation exposure						
Clinical Tests						
Device implantation						
Drug administration						
EEG, EKG, ECGetc						
Gene therapy, Genetic analysis						
Pregnancy/Breastfeeding Screening	$\boxtimes$					
Interview, Questionnaire, Diary, Survey (please attach)						
Stool collection, Urine collection, or any Non-surgical Specimen collection						
Surgical procedure or Specimen removal during surgery						
Tissue banking (complete Section 12)		· 🔲		· [		
Use of pre-existing tissues/specimens						
Other (list): fitting and treatment with MyoPro; upper limb motor learning therapy; H reflex (EMG), MRI, TMS	$\boxtimes$					

- \*Standard of care procedures are procedures performed in the course of normal medical care.
- \*\*Research Procedures are performed for the purposes of this research alone.

## 13. Please describe the research design and all study related procedures.

• Describe ALL PROCEDURES ASSOCIATED WITH THIS RESEARCH. This includes standard of care and research procedures.

• For complex studies please include diagrams and tables. Be sure to describe when each procedure will be performed. Be sure to provide information for each cohort, including normal controls).

The study requires 31 visits over 22 weeks and is divided into four parts: enrollment, orthotic fitting, therapy/training, and home use. See below table and description for details:

Part 1: Enrollment	Part 2: Orthotic Fitting		Part 3: Therapy/Training						Part 4: Home Use							Accessory to the second seconds			
Week 1	Weeks 2-3	Week S	Week 6	Week 7	Week 8	Week 9	Week 10	Week 11	Week 12	Week 13	Week 14	Week 15	Week 16	Week 17	Week 18	Week 19	Week 20	Week 21	Week 22
sment	íver ísíts)	2 x 1 hour sessions per week at LSCDVAMC Orthotic Assessment/Troi									Unsupervised at-home device use oubleshooting (as needed)								
Baseline Assessm	Cast, Fit, Del (minimum 3 v	1 x 2 hour Outcomes Assessment		1 x 2 hour Outcomes Assessment	X	1 x 3 hour Outcomes Assessment		1 x 2 hour Outcomes Assessment		1 x 4 hour Outcomes Assessment			1 x 2 hour Outcomes Assessment	X	X	1 x 2 hour Outcomes Assessment			1 x 3 hour Outcomes Assessment

Study Part 1 - Enrollment: The LSCDVAMC Institutional Review Board (IRB) requires consent both for screening and enrollment. Hence, after they provide screening consent, potential subjects will be screened to ensure that they meet the above criteria and are eligible to participate in the study. If eligibility criteria are met and the subjects provide enrollment consent, they will be enrolled in the study. The subjects will be evaluated and characterized at baseline and assessed at 2- or 3-week intervals for 18 weeks after orthosis delivery. Testing and outcome data collection will be done according to the schedule in Table 2 and in the section OUTCOME MEASURES

Study Part 2 – Orthotic Fitting: Myomo will provide three MyoPro Motion-G devices to be used through-out the study and the fit of each device will be customized for each subject. These devices will be used on a rotating basis during the study period which means that at the end of the participation in the study, a subject will return the MyoPro-G device to PI. A Certified Orthotist from either the Cleveland VA or from Myomo will custom fit all orthoses individually to each subject for optimum performance. This process will require up to three visits to cast, trial fit and deliver the orthosis.

During the fitting process, first a plaster mold of the subject's arm will be taken. This mold is used for custom orthosis construction and fabrication typically takes 2 weeks. Once the orthosis has been constructed, the subject will be brought back for a fitting. During this fitting, the device will be calibrated to the subject's individual muscle signal profile and minor adjustments to the orthosis can be made to optimize comfort.

Subjects will receive both powered elbow and grasp at the same time. Throughout the duration of the study, the study orthotist will be available once a week to check the fit of the device and troubleshoot any device issues as needed.

The MyoPro is a relatively new, commercially-available custom fabricated upper limb orthosis that is individually fabricated for the patient over a positive model of the patient requiring education, training, and experience to custom-fabricate. It has been cleared by the Food and Drug Administration (FDA) for home use without direct supervision of a therapist [26]. The

MyoPro Motion G features include a lightweight elbow orthosis with a surface electromyography (sEMG) sensor, a lightweight hand orthosis with a sEMG sensor, a "motion W" manually set multi-articulating wrist and a rechargeable battery. MyoPro's sEMG controlled software continuously monitors and senses, but does not stimulate, the affected muscles. The system then filters and processes data, which is sent to a motor to enable the desired motion. The process is similar to the way power steering helps a driver maneuver a car. Based on the subject's abilities, the system parameters are adjusted by the therapist or orthotist. The power assist only applies an amount of force proportional to what users exert naturally; this encourages them to apply and maintain all the strength and control they have to achieve a range of motion.

Study Part 3 –Therapy/Training: In addition to standard-of-care motor learning based therapy [33], we will follow the PERL ("Push Eat Reach Lift") Program recommended by Myomo, which consists of a 9 week, 18 session training plan. However, consistent with recommendations that best practices for the use of robotic devices be flexible, allowing therapists to tailor the therapy protocol and use of devices to an individual's level of motor impairment and rehabilitation goals [14], clinical judgment and subject progress will be used to either increase or decrease the number of therapy sessions and to determine the type of activities that are performed during training and therapy. Similar to Kim et al. [26], the sessions will be 1 hour typically 2 times a week but combine both therapy and training. Each week, there will be one session as needed that will combine therapy/training and orthotic assessment to ensure continued optimal fit and function of the device. Every second week, there will be one session that will combine therapy/training and outcomes evaluation.

The basic steps of the training program include:

- 1. Start in BICEP mode and HAND CLOSE mode. While seated, teach users to flex and extend the elbow while ignoring the hand, then switch and have them open and close the hand and ignore the elbow. Progress to sequential movements, e.g. close hand, bend elbow, open hand, relax elbow. Progress to simultaneous movements, e.g. flex elbow with closed hand; flex elbow with open hand; extend elbow with open hand; extend elbow with closed hand. This can all be repeated with the subject standing. This should be done two times a day for 10-15 minute sessions. Once these are mastered the subject can move to step 2.
- 2. Have the subject engage in task specific practice in BICEP and HAND OPEN modes. Tasks may include stacking cups or other items, grasping and moving items (e.g. cotton balls, items from purse or bag), hand to mouth tasks (e.g. bring napkin up to mouth, drink from cup or bottle), and finger extenders may be used to grasp paper, playing cards, take paper money out of a wallet. These activities should be attempted two times a day for five minutes each and progress to one time a day for 10 minutes each category. Once these are mastered the subject can move to step 3.
- 3. Have the subject engage in functional training. Identify the subject's goals: ADLs, instrumental ADLs, work or school related tasks, safety during ambulation and use of walking aide. Facilitate the subject's progression towards these goals: consider environmental set-up, utensils (including use of finger extenders) if needed.
- 4. Subject can progress to TRICEP and HAND OPEN modes when they demonstrate consistent Tricep and Forearm Extensor EMG signals, ability to relax forearm EMG and operate grasp in ALL wrist positions (flexed, neutral and extended), and proficiency with BICEP and HAND CLOSE modes, including simultaneous control. This should occur at approximately 1 month.

5. Subject can progress to DUAL mode when they demonstrate proficiency with BICEP/TRICEP and CLOSE/OPEN modes and they do not demonstrate significant co-contractions. This should occur at approximately 2 months. Subject may progress through the modes faster at the elbow, however it may be easier to use BICEP mode with HAND CLOSE mode, TRICEP mode with HAND OPEN mode and DUAL modes together.

Based on subject presentation, the above steps can also begin in TRICEP mode and progress from there. The above program requires at-home daily exercises by the subject, which will be prescribed by the therapist. Subjects will be deemed independent with device use once they or a caregiver are able to correctly demonstrate all the technical items listed on the device competency checklist (Table 1).

Table 1 MyoPro Motion-G Competency Checklist

Is the subject/caregiver able to demonstrate the following abilities appropriately regarding using the device:

- Apply and remove the pads
- Place straps on the device
- Secure orthosis on the arm
- Attain proper sensor placement on the bicep
- Attain proper sensor placement on the tricep
- Attain proper sensor placement on the forearm flexors
- Attain proper sensor placement on the forearm extensors
- Demonstrate proficiency manipulating the pronation/supination ring and the wrist hinge to position the distal extremity
- Turn the control unit on
- Choose BICEP/TRICEP/OPEN/CLOSE/DUAL modes
- Calibrate the device
- Change the low, medium and high settings
- Change between modes
- Remove orthosis from arm
- Use proper storage techniques
- Understands all safety precautions associated with operating the device

Is the subject/caregiver able to demonstrate the following abilities appropriately regarding the home treatment program:

- Safely and correctly performs all the given tasks
- Adjust the device to the correct settings for each task
- Independently performed the home treatment program at least one time
- Understands all safety precautions associated with device usage during activities

Study Part 4 – Home Use: Having demonstrated the above competencies, subjects will start a 9-week program practicing upper limb activities at home. Subjects will have reassessments in the clinic as needed to trouble-shoot any technical issues, monitor adverse events, and/or upgrade their home program. Every third week, there will be one session at the clinic for outcomes evaluation. The subject will record daily at home use of the device in a paper calendar log.

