#### **EXCLUSION CRITERIA:**

• Spasticity of both the flexors and extensors (defined as > 3 on MAS for both) and also the shoulder internal rotators [26]

- Shoulder subluxation, pain or dislocation
- Shoulder passive range of motion < 45 degrees in flexion and abduction
- Fixed upper limb contractures on the impaired arm and hand
- Unable to safely support the weight of their arm plus 4 lbs (1.82 kg) (the weight of the device) without pain
- Unable to safely bear a torque of 14 Newton Meters (Nm) or less on their elbow
- Less than 12 weeks since botulinum toxin injection in the impaired arm [26]
- New therapies/medications planned during study period
- Skin rash or open wound on impaired arm [26]
- Absent sensation (light touch or pain) on impaired arm
- Involuntary movements of the impaired arm [26]
- Pain or hypersensitivity in the impaired arm
- Inability to understand English

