# 40. Describe all procedures that minimize risks, please include study and standard of care procedures:

# Procedures that minimize Potential Foreseeable Risks-orthosis and study treatment/testing procedures

- The total duration of the study is about 31 visits over a period 22 weeks, which is a long commitment and increases risk of subject dropout. Subjects are informed of their time commitment during the screening phase and at enrollment consent and throughout their study participation.
- There is a possibility that some discomfort may arise while wearing the orthosis. Subjects will be required to wear the device for up to two hours during training and as long as tolerated at home. If at any time they feel uncomfortable, they are instructed to inform the researchers so that modifications can be made to the orthosis to improve comfort.
- There is a possibility that if the subject had ever experienced issues with shoulder instability or pain using the orthosis may cause these issues to flare up again Shoulder stability and pain will be monitored throughout the study to ensure that the device is not causing problems. Development of shoulder pain or additional subluxation during the course of the study would result in subject withdrawal from the study if modifications such as adding a shoulder harness were insufficient to overcome shoulder stability issues.
- The manufacturers of the orthosis have been careful to ensure that it is safe and cannot apply a dangerous amount of force to the arm or hand. Safety mechanisms have been implemented into the control software, the electronics hardware, and the mechanical hardware of the brace. For example, in the software commands that control the orthosis and the electronics of the orthosis, there are limits on the amount of force that can be commanded to the system. The mechanical system contains physical limits that prevent the orthosis from exerting force in an unsafe direction. In the worst case scenario, if all of these safety mechanisms fail, there is a small risk that the arm could be injured.

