- The orthosis incorporates stainless steel, non-allergenic surface electrodes with no adhesive. It is very rare that these electrodes will cause skin irritation, but they might if the subject has allergies to certain metals (not including nickel) and/or orthosis fit is not correct. Development of skin rashes or open wounds as a result of the orthosis that could not be overcome by modifications to fit or improved donning/doffing procedures would result in subject withdrawal from the study.
- Functional performance of the arm with the orthosis will be videotaped during some of the outcome evaluations. The subjects' upper body, head, and neck will be visible in the video tapes which increases the risk of loss of confidentiality. The tapes will be stored in a locked cupboard. The only people with access to the cupboard will be the treating therapist and [name].
- Fatigue during study interventions. During the therapy sessions and testing sessions, subjects could become fatigued during a given motor learning session. Subjects could experience mild muscle soreness associated with using muscles that have not been utilized for a number of months or years. Exercises will be progressed to patient tolerance and monitored both within and between sessions by the therapist.
- Risk management and emergency response
  - Subjects will be monitored at all study visits to ensure that there are no open wounds or skin rashes on the impaired arm and that the shoulder is not dislocated, subluxed or painful. If at any time during the use of the device, the subject notices any of the following, they should immediately discontinue use and seek guidance from the researchers:
  - Unusual noises from the orthosis (skipping, clicking, etc.)
  - Smells from the orthosis (smoking, burning plastic, etc.)

The investigators may stop a subject's participation in the study without their consent if they think that it will be in the best interest of the subject, if the subject does not follow the study plan, if the subject experiences a study-related injury, or for any other reason. If subjects sustain an injury as a direct result of the study, medical care will be provided by the Cleveland VA Medical Center at no cost to the subject. Financial compensation for such things as lost wages, disability, or discomfort due to an injury is not available.

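### In home use, up to 21 days can pass without a scheduled skin or shoulder check, and no prompted symptom record is described for the days between

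*Combined protocol and SAP*

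**What the plan says.** **Checks follow visits.** Item 40 (risk management) states: "Subjects will be monitored at all study visits to ensure that there are no open wounds or skin rashes on the impaired arm". The same sentence covers the shoulder. Item 40 also says the shoulder will be monitored throughout the study, without giving a frequency.

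**Visit schedule.** In Item 13, Part 3, the training programme is one "which consists of a 9 week, 18 session training plan", and "the sessions will be 1 hour typically 2 times a week but combine both therapy and training". The number of sessions may be raised or lowered on clinical judgment. For Part 4 the text is: "Every third week, there will be one session at the clinic for outcomes evaluation". Table 2 puts these visits at weeks 16, 19 and 22.

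**Between visits.** Part 4 allows as-needed clinic reassessments, with adverse-event monitoring among the reasons. Item 40 tells subjects to report discomfort whenever they feel it. Part 2 makes an orthotist available weekly throughout the study to check fit as needed. Item 48 says the therapist will be in touch with subjects throughout, in the context of answering questions.

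**Daily record.** "The subject will record daily at home use of the device in a paper calendar log". No other content is described.

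**Stop-and-call list.** Item 40 lists signs that should make the subject stop using the device at once and seek guidance. They are unusual noises and smells; the first entry begins "Unusual noises from the orthosis (skipping, clicking, etc". No skin or shoulder sign is listed.

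**Wear and sensation.** Item 40: "Subjects will be required to wear the device for up to two hours during training and as long as tolerated at home". The only sensory exclusion in Item 30 is "Absent sensation (light touch or pain) on impaired arm".

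**The concern.** Skin wounds or rash and shoulder pain or subluxation are the two device harms for which Item 40 gives withdrawal rules. In the home-use phase, which is largely unsupervised, scheduled looks at both become much rarer. Nothing described in the plan then asks about them between visits.

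The weight falls on the subject noticing a problem and volunteering it. That is a weaker safeguard here than in many trials. Reduced sensation is compatible with entry, and the discomfort instruction works only if the subject feels discomfort. Item 47 expects many participants to have a legal guardian. The OPUS satisfaction module does ask about skin irritation and pain from the device, and Item 13 notes that these are among the hardest items to endorse. Within home use, however, Table 2 schedules it only at week 22.

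At stake is the completeness of the safety record for unsupervised home use. An event that starts and settles between two visits enters the record only if someone mentions it.

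**Working it through.** **Inputs.** Table 2 assessment weeks are 5, 7, 9, 11, 13, 16, 19 and 22. Training is 18 sessions in 9 weeks (Item 13, Part 3). Home use is 9 weeks with one session every third week (Part 4). Checks happen at visits (Item 40).

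**Step 1: reproduce the plan's schedule.** Weeks 5 to 13 inclusive are 13 − 5 + 1 = 9 weeks; 9 × 2 = 18 sessions, as stated. Weeks 14 to 22 are 22 − 14 + 1 = 9 weeks. Differences between assessment weeks are 2, 2, 2, 2, 3, 3, 3. The plan's figures agree with each other.

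**Step 2: scheduled checks per phase.** Training 18, home use 3; 18 / 3 = 6, a six-fold drop over equal 9-week periods.

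**Step 3: longest scheduled gap.** Two visits a week leave gaps of 3 and 4 days. In home use the gaps (weeks 13 to 16, 16 to 19, 19 to 22) are each 3 × 7 = 21 days. The ratio lies between 21 / 4 = 5.3 and 21 / 3 = 7.

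**Step 4: average wait for the next scheduled check.** Assume onset is uniform in time and the subject does not report.
- Home use: 21 / 2 = 10.5 days.
- Training, alternating gaps of 3 and 4 days: (3² + 4²) / (2 × 7) = 25 / 14 = 1.8 days.

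**Step 5: illustration only.** The documents give no event duration, so D is assumed. With uniform onset and no reporting, an event of D days (D no more than 21) overlaps a three-weekly visit with probability D / 21.
- D = 3: 3 / 21 = 14%
- D = 5: 5 / 21 = 24%
- D = 10: 10 / 21 = 48%

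On the training grid an event of 4 days or more always meets a visit. One of 3 days does so with probability (3 + 3) / 7 = 86%.

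**Step 6: does any between-visit route act as a scheduled or prompted check?**

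| Route | Location | Fixed timing? | Prompts for skin or shoulder? |
|---|---|---|---|
| Report discomfort | Item 40 | No | No, subject must notice |
| Clinic reassessment | Item 13, Part 4 | No, as needed | Adverse events in general |
| Orthotist | Item 13, Part 2 | Weekly availability, used as needed | Device fit |
| Therapist contact | Item 48 | Frequency not stated | Not stated |
| Daily log | Item 13, Part 4 | Daily | None described |

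The log is the only one of these with fixed daily timing, and no symptom content is described for it.

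**The case against.** The plan has several safety nets. Besides the routes tabulated above, Item 30 requires home support if needed. The competency checklist (Table 1) has the subject or caregiver show understanding of the safety precautions before home use starts. Table 2 has a row for exactly these shoulder and skin harms, and after screening its entry starts by calling the monitoring ongoing. The device is described as cleared for home use without direct therapist supervision. The aims concern therapeutic and functional effects, so no harm rate is being estimated.

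Much of this stands, and it rules out stronger readings.
- A reader might infer that an injury will go unseen for 21 days. That requires every self-report and as-needed route to fail. The 21 days is a gap between scheduled checks only.
- A reader might infer that events healing between visits are never counted. A subject can report them at the time or at the next visit.
- A reader might infer that the log captures nothing but use. The form is not in the documents; they only describe no other field.
- A reader might call Part 4 the phase of highest exposure. No wear hours are given, home exercises are already required during training, and open-ended wear at home is not limited to Part 4. The stroke pilot in Item 8 saw under one hour a day.
- The twice-weekly figure is typical, not guaranteed.
- The stop-and-call list can be read as a list of device-malfunction signs, with skin and shoulder handled elsewhere in Item 40.

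The objection does not supply a fixed or prompted between-visit check. The Table 2 row is partly unreadable in the text available to this review, so what it prescribes between visits cannot be judged. The content of the safety precautions in the checklist is not stated.

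**Conclusion.** The point holds in a limited form. Scheduled staff checks of skin and shoulder fall six-fold in home use, from 18 to 3 over 9 weeks, and up to 21 days can pass without one. In between, detection rests on event-driven routes, none of which is described as a fixed or prompted skin or shoulder check. Transient events may therefore be under-recorded.

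The schedule arithmetic assumes the typical twice-weekly training pattern. The size of any under-recording is unknown. The 14% to 48% range rests on assumed durations of 3 to 10 days, uniform onset and no self-report; it is an illustration, not a finding. The primary efficacy analyses are not affected.

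One further matter needs clarifying. An open wound or rash bars entry under Item 30. On study, Item 40 leads to withdrawal only if changes to fit or to donning and doffing do not resolve it. Rules for entry and for conduct can legitimately differ, so this is not a contradiction in itself. But the passages read for this review do not say what applies between finding such a problem and completing the modifications.

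**What to change.** **Log.** Add three daily yes/no fields to the existing paper calendar log:
1. skin redness or wound seen;
2. shoulder or arm pain;
3. device use stopped because of either.

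Review the log at each visit and record positive entries as adverse events. If the form already has such fields, say so in Part 4.

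**Reconciliation.** The sponsor should reconcile Item 13 (Parts 2 and 4), Item 40, Item 48, the Item 30 wound criterion and the Table 2 row on skin and shoulder. The text should state what between-visit safety contact is planned, and what applies between finding a skin or shoulder problem and completing modifications. The content of that clinical rule is for the sponsor and investigator, and none is proposed here.

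**Cost.** One block on an existing form and some protocol wording, with no added visits or staff. The downside is slightly more daily logging for subjects and more review at visits.
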